3.0 PATIENT SELECTION

3.1 Inclusion Criteria

1. Histologically or cytologically confirmed diagnosis of squamous cell carcinoma of the head and neck.
2. Disease must be considered incurable. Incurable is defined as metastatic disease or a local or regional recurrence in a previously irradiated site that is unresectable (or patient declines resection).
3. Measurable disease defined as lesions that can be accurately measured in at least one dimension (longest diameter to be recorded) as ≥ 10 mm with CT scan, as ≥ 20 mm by

- chest x-ray, or ≥ 10 mm with calipers by clinical exam. (Phase I only: patients without measurable disease by RECIST 1.1 criteria but with evaluable disease by imaging or physical exam will be eligible as well.)
4. Phase I only: any (or no) prior therapy for metastatic disease is allowed, including cetuximab. If a patient has not received prior standard therapy, s/he must have been offered and refused prior standard therapy.
 5. Phase II only:
Arm 1: disease progression after at least one cycle of prior treatment with cisplatin or carboplatin for incurable disease. Prior treatment with cetuximab for incurable disease is not permitted.
Arms 2 and 3: disease progression after at least one cycle of treatment with cetuximab for incurable disease.
 6. Phase II only: at least one line of prior therapy for incurable disease.
 7. Phase II only:
Arms 1 and 2: disease must be determined to be HPV-unrelated. HPV-unrelated SCCHN is defined as either p16-negative OPSCC or non-OPSCC (larynx, hypopharynx, oral cavity) or p16-negative unknown primary SCC presenting with a level 2 or 3 neck node. p16 will be assessed by IHC; a specimen showing any staining will be considered p16-positive.
Arm 3: disease must be HPV-related SCCHN (defined as OPSCC or unknown primary presenting with a neck mass that is either p16 positive or HPV ISH or PCR positive).
 8. Minimum of 14 days elapsed since the end of any prior therapy.
 9. At least 18 years of age.
 10. Resolution of all acute toxic effects of prior anti-cancer therapy or surgical procedures to NCI CTCAE version 4.0 Grade ≤ 1 (except alopecia or other toxicities not considered a safety risk for the patient at investigator's discretion)
 11. ECOG performance status ≤ 2 (see Appendix A).
 12. Adequate bone marrow and organ function as defined below:
 - a. Absolute neutrophil count $\geq 1,500$ mm³
 - b. Platelets $\geq 100,000$ mm³
 - c. Hemoglobin > 9 g/dL

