5.6 Dosing for Phase II

Dosing for phase II will be administered as per Section 5.2. Dose of PD 0332991 will be 125 mg, which was the highest dose given in phase I (no MTD found). Thirty patients will

be enrolled to Arm 1 of phase II, 30 patients will be enrolled to Arm 2 of phase II, and 24 patients will be enrolled to Arm 3 of phase II. Enrollment for all arms may take place concurrently.

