9.2.2 Phase II

p16 by IHC will be performed on all patients to determine eligibility and arm assignment.

Analysis of cyclin D1 expression as well as total and phospho-Rb by IHC will be performed on all archived specimens.

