10.0 STUDY CALENDAR

Screening evaluations are to be conducted within 28 days prior to start of protocol therapy.

	Screening	Weekly during Cycle 1	Prior to Day 1 of each cycle (every 4 weeks Cycle 2 and beyond) ^p	EOT	F/U ^j
Physical exam	X	X	X	X	
Vitals signs	X	X	X ^a	X	
Performance status	X	X	X	X	
Adverse event assessment	X ----- X ^k				
CBC	X	X	X ^b	X	
Chemistry panel, LFTs ^f	X	X	X	X	
Pregnancy test	X			X	
EKG	X	X ^c	X ^c		
CT neck and chest	X ^d		X ^d		
Archival tissue	X ^m				
Optional tumor biopsy	X ^e		X ^e	X	
QOLs (Phase II only)	X		X ⁿ		
Blood for PKs ^o		Refer to Section 9.3			
PD0332991 ^g		X ----- X ^g			
Cetuximab ^h		X ----- X ^h			

^aVital signs should be taken weekly, even if treatment is held for toxicity. This can occur at chemotherapy visits when not having physical exams.

^bCBC to be performed weekly throughout all cycles, even if treatment is held for toxicity

^cEKG: Day 22 of each cycle

^dTumor assessments with CT of neck and chest will be performed at screening and at subsequent 8 week intervals (every 2 cycles).

^eTumor biopsies will be encouraged at baseline and at Cycle 2 Day 15-21 and at disease progression in patients in for Phase II patients (Arms 1 and 2 only). Cyclin D1, p16 by IHC, Ki-67, RNAseq, total and phospho-Rb and TUNEL assays will be performed on all three tissue sets.

^fChemistry includes Ca, Mg, K, Na, glucose, albumin, urea, creatinine; LFTs include ALT, AST, alkaline phosphatase, total bilirubin; please refer to Section 7.8 for special LFT AE reporting guidance.

^gPD0332991 will be taken orally on Days 1-21 of a 28 day cycle.

^hCetuximab will be administered weekly

^jFollow-up will consist of checks every 2 months (+/- 2 weeks) for recurrence and survival for 5 years; this may be done over the phone or as a review of the medical record.

^kAdverse events should be collected for 30 days after the last dose of study treatment.

^mp16, cyclin D1, and total and phospho-Rb will be assessed from FFPE tissue (15 slides, minimum of 4 accepted) on all patients (p16 to be done at screening; other testing to be performed at a later date)

ⁿAdminister QOLs at C2D1, C3D1, C4D1, and C6D1.

^oPhase I and Phase II Arm 1 only

^p+/- 2 day window for visits

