11.0 DATA SUBMISSION SCHEDULE

Case report forms with appropriate source documentation will be completed according to the schedule listed in this section.

Electronic data management systems will be used in this trial in collaboration with the Institute for Informatics at Washington University.

REDCap is a web-based clinical studies data management system that will be used for capture of clinical data from this trial. An electronic study calendar will drive the study's data collection workflow. Each participating center has access only to data from its own participants by creation of Data Access Groups. Washington University, as the data coordinating center, has access to data from all sites.

Case Report Form	Submission Schedule
Original Consent Form	Prior to registration
Demographics Form On Study Form On Study Prior Therapy Form Treatment Assignment Form	Prior to starting treatment
Treatment Form EKG Form	Every cycle
Adverse Event Form	Continuous
Tumor Biopsy Form PKs Form	Baseline and end of Cycle 2
QOLs Form	Baseline and at C2D1, C3D1, C4D1, and C6D1
Treatment Summary Form	Completion of treatment
Follow Up Form	Every 2 months for 5 years
Tumor Measurement Form	Baseline, end of every even numbered cycles, and end of treatment
MedWatch Form	See Section 7.0 for reporting requirements

Any queries generated by Washington University must be responded to within 28 days of receipt by the participating site. The Washington University research team will conduct a regular review of data status at all secondary sites, with appropriate corrective action to be requested as needed.

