rate (CR+PR) of 13% or lower would be unacceptable and an overall tumor response rate of 26% or higher would be of clinical interest. A total of 30 eligible and evaluable patients will be accrued to the phase II arm 2 portion of the study, and if 4 or more patients' tumors respond, the therapy will be accepted for further investigation. The design is based on Thall P and Sung H-G³⁸. The table and figure above also apply to phase II Arm 2.

For phase II Arm 3 portion, an overall tumor response rate (CR + PR) of 5% or lower would be unacceptable and an overall tumor response rate of 20% or higher of clinical interest. A total of 24 eligible and evaluable patients will be accrued to this arm. One or more tumor responses in the first 18 patients are required to continue enrollment. Two or more tumor responses in the first 24 patients are required to accept the alternative hypothesis. The design has probability = .74 of early stopping after the first cohort of 18 patients if the true response rate is 5% or less. The cumulative probability of completing the study (enrolling 24 patients) is 0.70 if the true response rate is 20% or greater. The design is based on Thall P and Sung H-G³⁸.

Number of patients	Cumulative probability of early stopping if response rate = 5% (null hypothesis)	Cumulative probability of early stopping if response rate = 20% (minimum alternative hypothesis)	Cumulative probability of continuing to end of study if response rate = 20% (minimum alternative hypothesis)
1	0	0	0
18	0.7436	0.2858	.7142
24	0.8335	0.2953	.7047

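### Does the overlap between the Arm 2 and Arm 3 HPV definitions call for a tie-break rule?

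*Combined protocol and SAP*

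**What the plan says.** All of the following is in the combined protocol and SAP.

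- **Arms 1 and 2 (Section 3.1, criterion 7):** "HPV-unrelated SCCHN is defined as either p16-negative OPSCC or non-OPSCC (larynx, hypopharynx, oral cavity) or p16-negative unknown primary SCC", the unknown primary having a level 2 or 3 node. Any p16 staining counts as positive. HPV ISH and PCR play no part.
- **Arm 3 (same criterion):** "defined as OPSCC or unknown primary presenting with a neck mass that is either p16 positive or HPV ISH or PCR positive".
- **Prior therapy (criterion 5):** "Arms 2 and 3: disease progression after at least one cycle of treatment with cetuximab for incurable disease". Arms 2 and 3 share this condition. Arm 1 bars prior cetuximab for incurable disease, so it cannot overlap Arm 3.
- **Timing (Section 5.6):** "Enrollment for all arms may take place concurrently".
- **Assignment test (Section 9.2.2):** "p16 by IHC will be performed on all patients to determine eligibility and arm assignment".
- **Screening (Section 10.0, footnote m):** "p16 to be done at screening; other testing to be performed at a later date". No section requires HPV ISH or PCR.
- **Decision rules (Section 15.0):** for Arm 2, 13% against 26%, acceptance at 4 or more responses in 30, with patient-by-patient response and toxicity limits ("The table and figure above also apply to phase II Arm 2"). For Arm 3, 5% against 20%, at least 1 response in the first 18 to continue, and acceptance at 2 or more in 24.

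**The concern.** The two HPV definitions ought to be complements, and they are not. One uses p16 only; the other uses p16 or either of two HPV tests. A patient whose results disagree can meet both, and since the prior-cetuximab condition is shared and the arms can be open together, nothing else in the eligibility criteria separates them. Section 9.2.2 seems to make matters worse. If p16 alone decides the arm, the ISH/PCR route into Arm 3 has no effect for oropharyngeal tumours or level 2/3 unknown primaries.

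The arms answer separate primary questions. A response is one quarter of the Arm 2 acceptance threshold (1 of 4) and one half of the Arm 3 threshold (1 of 2). Only Arm 2 has printed toxicity limits, and optional biopsies are offered in Arms 1 and 2 but not Arm 3. If two sites placed identical patients in different arms, each could cite the protocol, and the population behind each response rate would be slightly blurred.

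**Working it through.** **1. Is the overlap real?** Cross four sites with p16 (positive or negative) and HPV ISH/PCR (positive, or negative/not done): 4 x 2 x 2 = 16 profiles. The p16-positive column below covers two profiles per row.

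| Site | p16 positive, any HPV result | p16 negative, HPV negative or not done | p16 negative, HPV positive |
|---|---|---|---|
| Oropharynx | Arm 3 | Arm 2 | **both** |
| Larynx, hypopharynx, oral cavity | Arm 2 | Arm 2 | Arm 2 |
| Unknown primary, level 2/3 node | Arm 3 | Arm 2 | **both** |
| Unknown primary, neck mass elsewhere | Arm 3 | neither | Arm 3 |

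Two of 16 profiles meet both definitions.

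**2. Does Section 9.2.2 contradict criterion 7?** It says p16 is done on everyone to settle eligibility and arm. It does not say p16 alone. Both definitions use p16, so testing everyone is compatible with a further ISH/PCR route. Even if p16 did govern, one of the three p16-negative, HPV-positive profiles that Arm 3 admits would still enter by that route (unknown primary with a neck mass elsewhere). This is a silence about discordant results, not a contradiction.

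**3. How many patients?** No count is given. Section 1.1 says nearly all HPV-related oropharyngeal cancers stain strongly and diffusely for p16, and criterion 7 calls any staining positive. A dual-eligible patient therefore needs no staining, a positive result from a test that is not required, and progression on cetuximab.

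**4. What would they do to the conclusions?** The plan prints no figure for this point, so shares and rates here are assumptions: one or two such patients, at 8% or 13% in Arm 3 and at 5% or 8% in Arm 2. The 13% is the Arm 2 unacceptable rate and the 5% is the Arm 3 one; the 8% has no source.

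*Arm 3, rule as worded (stop at 0/18, accept at 2 or more of 24), all patients at 5%:*

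P(accept) = 1 - 0.95^18 - 18 x 0.05 x 0.95^17 x 0.95^6 = 1 - 0.3972 - 0.2766 = 0.326.

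Replace one patient by one at 13%:

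- Among the first 18: P(0 of 18) = 0.95^17 x 0.87 = 0.3638. P(1 of 18, then 0 of 6) = (0.95^17 x 0.13 + 17 x 0.05 x 0.95^16 x 0.87) x 0.95^6 = 0.2792. P(accept) = 0.357.
- Among the last 6: 1 - 0.3972 - 18 x 0.05 x 0.95^17 x 0.95^5 x 0.87 = 1 - 0.3972 - 0.2533 = 0.3495.
- Average over position: (18 x 0.357 + 6 x 0.3495)/24 = 0.355.

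*Arm 2, printed response limits (stop at 0 responses for n = 3-11, at 1 or fewer for 12-17, at 2 or fewer for 18-23, at 3 or fewer for 24-30), toxicity limits ignored, all patients at 13%:* exact recursion over patients gives P(accept) = 0.165.

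| Dual-eligible patients | Arm 3, at 8% | Arm 3, at 13% | Arm 2, at 5% | Arm 2, at 8% |
|---|---|---|---|---|
| none | 0.326 | 0.326 | 0.165 | 0.165 |
| one | 0.337 | 0.355 | 0.158 | 0.160 |
| two | 0.348 | 0.384 | 0.150 | 0.156 |

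Entries are averages over enrolment position. In Arm 2 position matters more because of the early response limits: two patients at 5% give 0.099 to 0.165. All of those lie at or below the base value, so in Arm 2 the error is towards caution.

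The early-stopping probability of 0.7436 printed for Arm 3 is not what a single look for 0/18 gives (0.397). That is a separate matter; here only differences under one fixed rule are used.

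**The case for a change.** The strongest case for a change is that rarity does not cure a gap in an assignment rule. The ISH/PCR wording is presumably there because someone expected to use it, a single response can decide whether Arm 3 continues past 18 patients, and one added sentence needs no new test or sample.

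The literal overlap and the missing tie-break stand. The rest is weaker.

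- **Discretion is limited.** Section 4.0 requires eligibility to be confirmed by Washington University before registration, and Section 4.1 asks for a signed checklist and source documents. One centre sees each case. The "Treatment Assignment Form" is due before treatment starts (Section 11.0), so the arm cannot be chosen on response.
- **The patient's treatment does not depend on the arm.** Section 5.6 sets one PD 0332991 dose for all of Phase II, and cetuximab follows Section 5.2 throughout.
- **Neither direction is clearly better.** Letting p16 govern fits its description in Section 1.1 as a surrogate for active HPV. Letting a positive HPV test govern keeps the Arm 3 route fully usable. But barring HPV-positive cases from Arm 2 alone would split a definition it shares with Arm 1. A rule would buy consistency for a handful of patients at most.

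**Conclusion.** The observation is correct but leads to no change. Criterion 7 leaves one narrow group, p16-negative and HPV ISH- or PCR-positive oropharyngeal or level 2/3 unknown primary disease, eligible for both Arm 2 and Arm 3, and Section 9.2.2 does not address it. This is missing detail that the coordinating centre can settle at registration. Analysts can identify any such patient from the recorded HPV results and arm assignment.

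Averaged over enrolment position, one such patient moves the false-acceptance probability by at most 0.029 in Arm 3 (0.326 to 0.355) and by less than 0.01 in Arm 2; two move it by at most 0.058 (0.326 to 0.384) and about 0.015 (0.165 to 0.150). These sizes rest on assumed numbers and response rates that the documents do not supply, and they are zero if the patients respond like the others in their arm. The judgement also assumes that discordant cases are as rare as Section 1.1 and the any-staining cut-off imply. On that footing, following the plan as written still gives sound conclusions for both arms.

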3.2 Exclusion Criteria

1. Phase II, Arm 1 only: prior treatment with cetuximab.
2. A history of other malignancy ≤ 1 year previous with the exception of basal cell or squamous cell carcinoma of the skin which were treated with local resection only, carcinoma *in situ* of the cervix, or synchronous H&N primaries.
3. Currently receiving any other investigational agents.
4. Patient must not have a history of or clinical evidence of central nervous system metastases or leptomeningeal carcinomatosis, except for individuals who have had previously-treated CNS metastases, are asymptomatic, and have had no requirement for steroids or anti-seizure medications (with the exception of Keppra) for 1 month prior to first dose of PD 0332991.
5. A history of allergic reactions attributed to compounds of similar chemical or biologic composition to PD 0332991, cetuximab, or other agents used in the study.
6. Treated within the last 7 days prior to Day 1 of protocol therapy with:
 - a. Food or drugs that are known to be CYP3A4 inhibitors (e.g. grapefruit juice, verapamil, ketoconazole, miconazole, itraconazole, erythromycin, clarithromycin, telithromycin, indinavir, ritonavir, nelfinavir, atazanavir, amprenavir, nefazodone, diltiazem, and delavirdine) or inducers (i.e. dexamethasone, glucocorticoids, progesterone, rifampin, phenobarbital, St. John's wort). (See Appendix D)
 - b. Drugs that are known to prolong the QT interval.
 - c. Drugs that are proton pump inhibitors.
7. Uncontrolled electrolyte disorders that can compound the effects of a QTc-prolonging drug (e.g., hypocalcemia, hypokalemia, hypomagnesemia)

8. Uncontrolled intercurrent illness including, but not limited to, ongoing or active infection symptomatic congestive heart failure, unstable angina pectoris, cardiac arrhythmia, or psychiatric illness/social situations that would limit compliance with study requirements.
9. Pregnant and/or breastfeeding. Women of childbearing potential must have a negative serum pregnancy test within 28 days of study entry. Female patients must be surgically sterile or be postmenopausal, or must agree to use effective contraceptive during the period of the trial and for at least 90 days after completion of treatment. The decision of effective contraception will be based on the judgment of the principal investigator or a designated associate.
10. Phase I and Arm 1 of Phase II: Known HIV-positivity and on combination antiretroviral therapy because of the potential for pharmacokinetic interactions with PD 0332991. In addition, these patients are at increased risk of lethal infections when treated with marrow-suppressive therapy. Appropriate studies will be undertaken in patients receiving combination antiretroviral therapy when indicated.
Arms 2 and 3 of Phase II: patients with HIV infection and antiretroviral therapy are not excluded, as there are no pharmacokinetic tests being performed.

3.3 Inclusion of Women and Minorities

Both men and women and members of all races and ethnic groups are eligible for this trial.

4.0 REGISTRATION PROCEDURES

Patients must not start any protocol intervention prior to registration through the Siteman Cancer Center.

The following steps must be taken before registering patients to this study:

1. Confirmation of patient eligibility by Washington University
2. Registration of patient in the Siteman Cancer Center OnCore database
3. Assignment of unique patient number (UPN)

Once the patient has been entered in the Siteman Cancer Center OnCore database, the WUSM coordinator will forward verification of enrollment and the UPN via email.

4.1 Confirmation of Patient Eligibility

Confirm patient eligibility by collecting the information listed below and scanning and emailing it to the research coordinator listed in the *Siteman Cancer Center Clinical Trials Core Protocol Procedures for Secondary Sites* packet at least one business day prior to registering patient:

1. Your name and contact information (telephone number, fax number, and email address)
2. Your site's PI's name, the registering MD's name, and your institution name
3. Patient's race, sex, and DOB
4. Three letters (or two letters and a dash) for the patient's initials
5. Currently approved protocol version date
6. Copy of signed consent form (patient name may be blacked out)
7. Planned date of enrollment
8. Completed eligibility checklist, signed and dated by a member of the study team
9. Copy of appropriate source documentation confirming patient eligibility

4.2 Patient Registration in the Siteman Cancer Center OnCore Database

Registrations may be submitted Monday through Friday between 8am and 5pm CT. Urgent late afternoon or early morning enrollments should be planned in advance and coordinated with the Washington University research coordinator. Registration will be confirmed by the research coordinator or his/her delegate by email within one business day. Verification of eligibility and registration should be kept in the patient chart.

All patients at all sites must be registered through the Siteman Cancer Center OnCore database at Washington University.

4.3 Assignment of UPN

Each patient will be identified with a unique patient number (UPN) for this study. Patients will also be identified by first, middle, and last initials. If the patient has no middle initial, a dash will be used on the case report forms (CRFs). All data will be recorded with this identification number on the appropriate CRFs.

5.0 TREATMENT PLAN

5.1 Premedication for Cetuximab

In an effort to prevent a hypersensitivity reaction, all patients should be premedicated with diphenhydramine hydrochloride 50 mg (or an equivalent antihistamine) IVPB given at least 30 minutes prior to cetuximab. Premedication may also include one liter of normal saline, hydrocortisone 100 mg IVPB, and/or albuterol inhalation (by nebulizer or inhaler) according to standard of care procedures.

5.2 Agent Administration

PD 0332991 should be taken by mouth on Days 1 through 21 of each 28-day cycle. **Patients should take PD 0332991 capsules with food.** Patients will be required to keep

a drug diary (Appendix B).

If a patient misses a day's dose entirely, s/he must be instructed not to make it up the next day but to just take his/her regular dose the following day. If a patient vomits any time after taking a dose, s/he must be instructed not to make it up but to resume subsequent dosing the next day as prescribed. If a patient inadvertently takes an extra dose during a day, s/he must be instructed to not take the next day's dose.

Cetuximab will be administered intravenously on a weekly schedule. The first dose of cetuximab will be 400 mg/m²; every week thereafter, patients will receive a dose of 250 mg/m². Patients will continue to receive weekly cetuximab at 250 mg/m² for the duration of their participation on study.

Upon IRB/EC approval of Amendment 5, a PD 0332991 oral solution will be available for patients who cannot swallow the PD 332991 capsules. Patients who begin the study receiving the oral solution will remain on the oral solution for the duration of their time on treatment in the study. Patients, who begin the study receiving capsules but develop difficulty swallowing the capsules and did not have disease progression, will be allowed to switch to the PD 0332991 oral solution. These patients will then remain on the oral solution for the duration of their time on treatment in the study. Each clinical site will be provided the oral solution Investigational Product Manual (IPM) containing the dosage and administration instructions (DAI) for preparation of the PD 0332991 oral solution. **Patients can take PD 0332991 oral solution with or without food.**

